10.4.2. Secondary Endpoints

- The ORR will be assessed by investigator (for Phase 1) and by IRC (for Phase 2b) according to the IMWG criteria and is defined as the proportion of subjects who achieve a PR or better over the course of the study.
- The DOR is defined as the interval between the date of initial documentation of a response and the date of first documented evidence of progressive disease as assessed by investigator (for Phase 1) and by IRC (for Phase 2b), death, or date of censoring if applicable, for responders only. Subjects who start new anti-cancer treatment before documentation of disease progression will be censored on the date of the last adequate disease assessment that is on or before the start date of new anti-cancer therapy. Responders are subjects in the ITT population who achieve PR or better according to the IMWG response criteria. Non responders (\leq MR) will be excluded from the analysis for DOR.
- Clinical benefit rate (CBR) and its duration as assessed by investigator (for Phase 1) and by IRC (for Phase 2b) including subjects with minimal response (MR) or better according to the IMWG.
- OS is defined as the time from date of randomization until date of death due to any cause. Subjects who are known to be alive or whose survival status is unknown will be censored at the date last known to be alive. Subjects who are completely lost to follow-up for survival after randomization will be censored at randomization date (Phase 2b).
- TTP is defined as the time from the start of treatment until date of disease progression as assessed by IRC. Subjects who die before disease progression due to causes other than progression will be censored at the date of death (Phase 2b).

10.4.3. Efficacy Assessments by Investigator

Investigator-assessed PFS, ORR, DOR and CBR and its duration will be analyzed in a similar fashion as corresponding endpoints assessed by the IRC for Phase 2b.

10.4.4. Exploratory Endpoints

Exploratory endpoint analyses will be described in the SAP and may include the following:

- Time-to-next-treatment (TTNT) (Phase 2b)
- Patient reported outcomes (PROs) and disease-related symptoms according to EORTC QLQ-MY20 and EQ-5D-5L (Phase 2b)

10.5. Analysis Methods

10.5.1. Analysis for Phase 1

The Phase 1 portion of this study is an algorithm-based dose-escalation design to find the MTD/MAD and the Phase 2b dose of the ibrutinib, pomalidomide and dexamethasone combination and to characterize the most frequent AEs experienced through Phase 1 and the DLTs. Dose-limiting toxicities will be evaluated and will include all AEs experienced through Cycle 2 Day 1 pre-dose assessments.

The Phase 1 secondary efficacy endpoints are the ORR, DOR, and the CBR and its duration according to the IMWG response criteria. The point estimate of the rate and the corresponding exact binomial 95% confidence interval (CI) will be calculated. For DOR, the distribution of DOR as assessed will be provided using Kaplan-Meier method for responders. The CBR (\geq MR) and its duration will be analyzed similar to the analysis of ORR and DOR, respectively.

10.5.2. Primary Efficacy Analyses

Progression free survival is defined as the time from the date of randomization to IRC confirmed disease progression per IMWG response criteria or death from any cause, whichever occurs first. Subjects who withdraw from the study or are considered lost to follow-up without prior documentation of disease progression will be censored on the date of the last adequate disease assessment. Subjects who are progression-free and alive at the time of clinical cut-off, or have unknown status will be censored on the date of the last adequate disease assessment. For subjects without an adequate post-baseline disease assessment, PFS will be censored on the date of randomization. Adequate disease assessment is defined according to the IMWG criteria.

The analysis of PFS will be performed on Phase 2b subjects in the ITT population to compare PFS for the 2 treatment arms using a stratified log-rank test stratified by the number of prior lines of therapy (2-3 versus \geq 4), last prior treatment (no proteasome inhibitor [PI] or immunomodulatory agent [IMiD] versus PI or IMiD versus PI and IMiD) and age (\leq 75 versus $>$ 75 years). Distribution of PFS will be summarized for each treatment arm using the Kaplan-Meier estimate of median and its corresponding 95% CI. The estimate of the hazard ratio and its corresponding 95% CI will be computed using a Cox proportional hazards model stratified by the randomization stratification factors, the number of prior lines of therapy (2-3 versus \geq 4), last prior treatment (no PI/IMiD versus PI or IMiD versus PI and IMiD) and age (\leq 75 versus $>$ 75 years).

10.5.3. Secondary Efficacy Analysis

Overall response rate (ORR [PR or better]) as assessed by IRC, and its 95% CI will be calculated using normal approximation to the binomial distribution for the ITT population. Overall response rate will also be compared between 2 treatment arms (A and B) using the Cochran-Mantel-Haenszel chi-square test, stratified by the three stratification factors: number of prior lines of therapy, most recent line of therapy, and age.

DOR will be analyzed for subjects who achieve response (PR or better) based on the response assessed by IRC during the study. The distribution of DOR will be estimated using the Kaplan-Meier method similar to PFS.

The CBR and its duration, including subjects with MR or better, will be analyzed similar to the analysis of ORR and DOR, respectively.

PFS, ORR, DOR, CBR, and TTP will also be evaluated based on Investigator's assessments.

OS will be analyzed in the ITT population to compare OS for the 2 treatment arms (A and B) using a stratified log-rank test, stratified by the number of prior lines of therapy, last prior treatment and age. Distribution of OS will be summarized for each treatment arm using the Kaplan-Meier estimate of median and its corresponding 95% CI. Survival rate at landmark points will be summarized based on Kaplan-Meier point estimates.

All or some of the efficacy analyses may be performed based on the response-evaluable population as sensitivity analyses. A sensitivity analysis of PFS may be conducted with censoring at subsequent therapy if initiated prior to a documented PD.

10.5.4. Exploratory Efficacy Analysis

The distribution of TTNT will be estimated using the Kaplan-Meier method. Analysis method will be detailed in the SAP (Phase 2b).

Descriptive statistics for change in scores from baseline to each assessment time point will be summarized for the PROs and disease-related symptoms according to EORTC QLQ-MY20 and EQ-5D-5L (Phase 2b).

10.5.5. Open-Label Sub-study Treatment Arm C Efficacy Analysis (Phase 2b)

The primary efficacy endpoint is the ORR as assessed by IRC according to the IMWG response criteria. The hypothesis that the true ORR is $\leq 5\%$ (H_0) will be tested against $\geq 18\%$ (H_a), based on the exact binomial test. The point estimate of the rate and the corresponding exact binomial 95% CI will be calculated. For DOR, the distribution of DOR will be provided using Kaplan-Meier estimates for responders.

10.5.6. Pharmacokinetics

Plasma concentrations of ibrutinib and its metabolite (PCI-45227) and pomalidomide will be determined using a validated analytical method. Other potential metabolites of ibrutinib may be explored.

Bioanalytical data from this study will be used in noncompartmental PK analysis and also may be combined with data from other studies performed with ibrutinib in subjects with hematologic malignancies as part of a population PK analysis using nonlinear mixed effects models. For the population PK analysis of ibrutinib, covariates that could potentially correlate with plasma PK parameters will be evaluated. Pharmacokinetic relationships to pharmacodynamic measures of efficacy or toxicity may also be explored. The results of the population PK analyses will be presented in a separate report.

10.5.7. Biomarkers

- Exploratory identification of gene expression profiles, signaling pathways or biomarkers that may predict sensitivity or resistance to ibrutinib.
- Frequency of tumor mutations (or other molecular markers) between pre and post treatment tissue that may predict acquired resistance.

Clinically relevant biomarkers of high penetrance with presence/absence of mutation may be highly associated with clinical response. A Fisher Exact Test may be used to compare the clinical response rates between the mutant and wild-type populations for each biomarker.

10.6. Safety Analysis

Analysis of safety data will be conducted on the safety population, which includes enrolled subjects who receive at least 1 dose of study treatment. The baseline value for safety assessments will be defined as the last value on or before the day of the first dose of study drugs.

The safety variables to be analyzed include AEs, survival status, clinical laboratory test results (hematology and chemistry), ECOG performance status, physical examination findings, and vital signs measurements. Exposure to study treatment and reasons for discontinuation from study treatment will be tabulated. In general, continuous variables will be summarized using descriptive statistics (n, mean, median, standard deviation, standard error and range). Categorical variables will be summarized using frequencies and percentages. No formal statistical testing is planned.

Phase 1

All AEs experienced from the start of treatment through Cycle 2 Day 1 pre-dose assessments will be evaluated by the independent DMC for the purpose of identifying any DLTs during the identification of the MTD/MAD. In addition, detailed tabulation of safety data (AEs, clinical laboratory tests and other safety endpoints) will be summarized.

Phase 2b

Detailed tabulations of safety data (AEs, clinical laboratory tests and other safety endpoints) will be summarized by treatment arms for all subjects receiving the study drug. Summary statistics will include means, standard deviations, and medians for continuous variables and proportions for categorical variables. Safety analysis for Treatment Arm C will be conducted similar but described separately and independent from the safety analysis conducted for the randomized portion of the study.

In addition, a pooled safety analysis will be performed on all subjects receiving the combination of ibrutinib, pomalidomide and dexamethasone, which includes subjects in Phase 1 treated at the MTD/MAD, as well as those treated on Arms A and C of Phase 2b. This will be conducted

similar but described separately and independent from the safety analysis conducted for the randomized portion of the study.

Adverse Events

Adverse event parameters to be evaluated are the type, incidence, and intensity of AEs; the relationship of AEs to study treatment; and the action taken with respect to study treatment due to AEs.

The verbatim terms used in the eCRF by Investigators to identify AEs will be coded using the Medical Dictionary for Regulatory Activities (MedDRA) and graded according to [NCI CTCAE version 4.03](#). Treatment-emergent adverse events are those AEs occurring after the first dose of study treatment and within 30 days following the last dose of study treatment (ibrutinib, pomalidomide, or dexamethasone, whichever occurs later), but before first dose date of subsequent anti-cancer therapy, whichever occurs first; any AE that is considered study drug-related regardless of the start date of the event; or any AE that is present at baseline but worsens after the first administration of study treatment in severity or is subsequently considered drug-related by the Investigator.

All TEAEs will be included in the analysis. The number and percent of subjects with TEAEs will be summarized by system organ class and preferred term. Drug related AEs, SAEs, Grade ≥ 3 AEs, AEs leading to study treatment discontinuation, dose modification, or death, and events of special interest will be summarized and listed.

Clinical Laboratory Tests

Laboratory tests will be summarized separately for hematology and serum chemistry. All laboratory values will be graded using the [NCI CTCAE \(version 4.03\)](#). The worst toxicity grade during the study will be tabulated.

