4.1. Inclusion Criteria

To be enrolled in the study, each potential subject must meet all of the following inclusion criteria.

Disease Related

1. Subjects with relapsed/refractory MM who have received at least two prior lines of therapy ([Appendix 4](#)) including lenalidomide (LEN) and either bortezomib or carfilzomib and have demonstrated disease progression on or within 60 days of the completion of the most recent treatment regimen.
 - Subjects must have received at least 2 cycles of treatment with LEN and either bortezomib or carfilzomib at the approved dose and schedule (maintenance will be excluded).
2. Measurable disease defined by at least ONE of the following:
 - Serum monoclonal protein (SPEP) ≥ 1 g/dL.
 - Urine monoclonal protein (UPEP) ≥ 200 mg by 24 hour urine.

Laboratory

3. Adequate hematologic function independent of platelet transfusion and growth factor support for at least 7 days prior to Screening and dosing (Phase 1) or randomization/enrollment (Phase 2b), with the exception of pegylated G-CSF (granulocyte-colony stimulating factor pegfilgrastim) and darbopoeitin which require at least 14 days, defined as:
 - Absolute neutrophil count ≥ 1500 cells/mm³ (1.5×10^9 /L).
 - Platelet count $> 75,000$ cells/mm³ (75×10^9 /L).
 - Hemoglobin ≥ 8.0 g/dL.
4. Adequate hepatic and renal function defined as:
 - Serum aspartate transaminase (AST) or alanine transaminase (ALT) ≤ 3.0 x upper limit of normal (ULN).

- Serum creatinine < 3.0 mg/dL AND Creatinine Clearance ≥ 30 mL/min (by Cockcroft-Gault estimation OR as measured by 24 hour urine collection).
 - Total Bilirubin ≤ 2.0 mg/dL (unless bilirubin rise is due to Gilbert's syndrome or of non-hepatic origin).
5. PT/INR ≤ 1.5 x ULN and PTT (aPTT) ≤ 1.5 x ULN (unless on warfarin, then INR ≤ 3.0).

Demographic

6. Men and women ≥ 18 years of age.
7. Eastern Cooperative Oncology Group (ECOG) performance status of ≤ 2

Ethical/Other

8. All study participants must be registered into the mandatory Pomalyst REMS™ program or RevAid® program, and be willing and able to comply with the requirements of the Pomalyst REMS™ program or RevAid® program as appropriate for the country in which the drug is being used (**for US/Canada sites only**).
9. Female subjects of childbearing potential (FCBP^a) must adhere to the scheduled pregnancy testing as required in the Pomalyst REMS™ program or RevAid® program as appropriate for the country in which the drug is being used. (**for US/Canada sites only**).

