1 INTRODUCTION

The Study PCYC-1138-CA consisted of a Phase 1 and a Phase 2 part. After completion of the Phase 1 part, in which 11 subjects received study treatment, the sponsor decided to not pursue an indication for treatment of patients with multiple myeloma with ibrutinib and therefore terminate the study early. Thus, this statistical analysis plan (SAP) is to define only the key study elements for the Phase 1 part of the study including variable definitions, and statistical methods for analysis of data in evaluation of efficacy and safety. Analyses of pharmacokinetics data will be addressed in a separate document. Biomarker analysis will not be performed due to early termination of the study. Throughout this SAP, “study treatment” and “study drug” are used interchangeably.

Analysis methods specified in this document take precedence over those described in the study protocol should there be any difference.

1.1 Study Design – Phase 1

The Phase 1 part of the study was an open-label, international, multicenter dose-finding study of the ibrutinib, pomalidomide and dexamethasone combination in subjects with relapsed/refractory multiple myeloma (MM). Up to 18 patients were to be enrolled in order to determine the maximum therapeutic dose/maximum administered dose (MTD/MAD). In the dose finding portion of the study, up to 2 cohorts were to be explored (Table 1). The study followed a 3+3+3 dose escalation design. The MTD/MAD was defined as the highest dose level at which <33% (ie, ≤ 1 of 6 or ≤ 2 of 9) of subjects in a cohort experience a study treatment related dose limiting toxicity (DLT).

Table 1: Dosing Levels and Cohorts

Dose Level	Cohort	Ibrutinib ^a	Pomalidomide ^b	Dexamethasone ^c
-1	-1	420 mg once daily	4 mg	40 mg
1 (Starting Dose)	1	560 mg once daily	4 mg	40 mg
2	2	840 mg once daily	4 mg	40 mg

^a. Ibrutinib was administered PO starting on Day 1 of Cycle 1, dosing was continuous thereafter (without interruption).

^b. Pomalidomide was administered PO on Days 1 – 21 of a 28-day cycle.

^c. Dexamethasone was administered PO once weekly. The dose was reduced to 20 mg weekly in those >75 years of age

1.2 Objective/Endpoints of Study – Phase 1

- **Primary Objective**

- To determine the MTD)/ MAD of the ibrutinib, pomalidomide and dexamethasone combination.
- To determine the safety and tolerability of ibrutinib in combination with pomalidomide and dexamethasone in subjects with relapsed/refractory MM.

- **Secondary Endpoints**

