5 SAFETY ASSESSMENTS

Safety data will be summarized for safety population unless otherwise indicated. Table 3 summarizes the safety analyses to be carried out. AEs will be coded in accordance with the Medical Dictionary for Regulatory Activities (MedDRA). Severity of AEs were graded by the investigator according to the NCI Common Terminology Criteria for Adverse Events (NCI-CTCAE) v4.03. A listing will be provided to indicate dose-limiting toxicity (DLT).

In general, the treatment-emergent period is defined as the period from the date of the first dose of study treatment up to 30 days after the date of the last dose of study treatment or the day before initiation of subsequent anticancer therapy, whichever comes first. Treatment emergent AEs are those events that occur or worsen during the treatment-emergent period or that are related to the study treatment or events with a complete missing onset date but with a resolution date during the treatment phase.

All laboratory values will be converted to and reported as international standard (SI) units. In general, only data from the central laboratory will be summarized and analyzed. Laboratory parameters will be graded using the NCI CTCAE v4.03.

Table 3: Summary of Safety Assessments

Assessment Type	Definition	Analysis Methods
AE	TEAEs, SAEs, non-serious TEAE, grade 3 or worse TEAEs, related TEAEs, TEAEs leading to treatment discontinuation, TEAEs leading to dose reduction, TEAEs leading to death, protocol- defined events of special interest and other safety observations	Descriptive summary statistics and/or listings
Lab	Worst post-baseline toxicity grade for selected CTCAE gradable hematology and chemistry. Abnormalities in creatinine clearance, uric acid, and liver function	Descriptive summary statistics and/or listings
Vital Signs and other Observations Related to Safety	SBP, DBP, weight, heart rate, new or worsened eye-related symptoms	Descriptive summary statistics and/or listings
Dose Limiting Toxicity (DLT)	DLT	Listing

TEAE: treatment-emergent adverse event; SAE= serious adverse event; SBP: systolic blood pressure; DBP: diastolic blood pressure; CTCAE= Common Terminology Criteria for Adverse Events.

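### The SAP laboratory table gives the worst post-baseline grade without the baseline grade, so an abnormality carried in at entry cannot be told from a new or worsened one

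*Protocol*

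**What the plan says.** Protocol section 10.6, under Clinical Laboratory Tests, grades all laboratory values by CTCAE 4.03 and states: "The worst toxicity grade during the study will be tabulated". The Lab row of SAP Table 3 (section 5) specifies instead "Worst post-baseline toxicity grade for selected CTCAE gradable hematology and chemistry", as summary statistics and/or listings. The SAP governs where the two differ: "Analysis methods specified in this document take precedence over those described in the study protocol should there be any difference" (SAP section 1).

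Protocol 10.6 also fixes a reference point: "The baseline value for safety assessments will be defined as the last value on or before the day of the first dose of study drugs". Neither laboratory grade rule uses it. No shift table, display of baseline grade or worsening condition for laboratory grades appears in either document.

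Elsewhere the plan does look back to baseline. SAP section 5 begins its adverse event definition: "Treatment emergent AEs are those events that occur or worsen during the treatment-emergent period". Protocol 10.6 counts "any AE that is present at baseline but worsens after the first administration of study treatment in severity". SAP Table 3 itself limits eye-related symptoms to those that are new or have worsened.

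**The concern.** Subjects may enter with abnormal laboratory values. Protocol section 4.1 asks for "Adequate hematologic function independent of platelet transfusion and growth factor support", but sets the limits at "Hemoglobin ≥ 8.0 g/dL" and platelets above 75,000/mm³. It also allows AST or ALT up to 3 times the upper limit of normal, and creatinine just under 3.0 mg/dL with clearance from 30 mL/min. Exclusion criterion 11 lets toxicity from earlier treatment remain at Grade 1 or at the levels the entry criteria permit. Section 1.1 describes anemia, thrombocytopenia and neutropenia as consequences of myeloma itself.

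Under the SAP rule, a subject whose abnormal value never moves appears in the table at that grade. Another subject who was normal at entry and reached the same grade on treatment appears identically. Safety and tolerability is a primary Phase 1 objective. Phase 2 was not started, so there is no control arm to show the background rate. Cytopenias are also listed as known effects of ibrutinib (section 1.2.4.3) and of pomalidomide with dexamethasone (section 1.3.2), so these are the parameters for which the table most needs to separate entry status from change on treatment.

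**Working it through.** The plan states no figure to reproduce. The check is a reading of the rules side by side, followed by simple arithmetic on 11 subjects.

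**1. Which rule operates.** The protocol wording, read literally, could take in Screening values. The SAP restricts the table to post-baseline values and takes precedence. An entry abnormality that resolves before the first post-baseline sample is therefore not counted; one that persists is counted at its full grade.

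**2. Which grades can be carried over.** The documents give these cut-offs:

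| Parameter | Entry limit (4.1) | Cut-off given | Consequence |
|---|---|---|---|
| Platelets | above 75,000 | Grade 3 below 50,000 (5.4.4) | Grade 3 or 4 cannot be carried in |
| Neutrophils | at least 1,500 | Grade 4 below 500 (5.1.1, 5.4.4) | Grade 4 cannot be carried in |
| Hemoglobin | at least 8.0 g/dL | none given | carried grade not derivable |
| AST/ALT | up to 3 x ULN | none given | above normal allowed; grade not derivable |
| Creatinine | below 3.0 mg/dL | none given | carried grade not derivable |

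Section 8.3 requires Phase 1 subjects with Cycle 1 Day 1 laboratory tests to satisfy eligibility still before dosing, so the first two limits also apply to the baseline value. Parameters with no entry limit, such as potassium, phosphate and uric acid, have no such protection.

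**3. Size per subject.** SAP section 1 reports 11 treated subjects. One carried-over abnormality adds 1/11 = 9.1 percentage points to the row for that parameter.

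**4. How likely it is to matter (assumed inputs).** Let p be the share of subjects whose graded entry abnormality persists and never rises. The documents give no value for p. The expected number is 11p, and the chance of at least one is 1 − (1 − p)^11:

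- p = 0.10: 1.1 subjects; 1 − 0.90^11 = 69%
- p = 0.25: 2.75 subjects; 1 − 0.75^11 = 96%
- p = 0.50: 5.5 subjects; 1 − 0.50^11 = above 99.9%

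**5. What the two displays would show (assumed inputs).** Let b be the share entering with an abnormality that does not resolve, and q the chance of a new or worsened grade, taken as equal in all subjects. The any-grade rate in the planned table is b + (1 − b)q; a count of grades above baseline gives q. With q = 0.30:

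- b = 0.10: 0.10 + 0.90 × 0.30 = 37.0%, against 30%
- b = 0.25: 0.25 + 0.75 × 0.30 = 47.5%, against 30%
- b = 0.50: 0.50 + 0.50 × 0.30 = 65.0%, against 30%

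**The case against.** The strongest reply is that little rests on this table. Under protocol section 7.1.6, laboratory abnormalities that the investigator judges clinically significant are recorded as adverse events. Under section 11.1.1, a pre-existing condition is not an adverse event unless it worsens in severity, frequency or character. The SAP reports treatment-emergent, Grade 3 or worse, and related events, and events leading to dose reduction or discontinuation, separately. The MTD/MAD rests on dose-limiting toxicities. Listings are permitted, and no formal testing of safety data is planned. All of this stands and limits the point to one row of one table. A listing may let a reader reconstruct baseline status, but nothing requires it to, and it does not change a summary percentage.

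Three stronger readings are tempting, and the documents do not support them.

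- A reader might infer that the table counts entry disease as drug toxicity and so overstates the toxicity of the combination. The SAP neither calls these grades treatment-emergent nor attributes them to the drugs. It describes post-baseline values; attribution would be the reader's own step.
- A reader might infer that adverse events and laboratory grades follow opposite rules. They differ, but the SAP adverse event definition also admits treatment-related events, and events with a wholly missing onset date that resolve during treatment, without a worsening test.
- A reader might put a figure on entry anemia: 30% to 60% would give about 3 to 7 of 11 subjects. The documents contain no such prevalence and no hemoglobin grade cut-offs.

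A rule based only on a rise in grade also has a cost. It misses a decline within a grade, and a value that improves and then falls back to its baseline grade on treatment.

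**Conclusion.** The point holds in a limited form. The governing laboratory rule omits the baseline grade, so in 11 single-arm subjects the table cannot separate a persisting entry abnormality from a new or worsened one. Each such subject is worth 9.1 percentage points; how many there are is not known from the documents, and the percentages in the working beyond that one are illustrations on assumed inputs. For platelets and neutrophils, the carry-over is confined to grades below those that the entry limits rule out. Adverse event tables and dose-limiting toxicity decisions are not affected.

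Severity is low: the output is descriptive, the sample is small and the program has been terminated. It is still worth doing, because safety is a primary objective and the remedy is cheap.

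One condition is a separate matter. SAP section 5 says that, in general, only central laboratory data are summarized, while protocol sections 7.3.1 and 7.3.2 have hematology and chemistry done locally. These must be reconciled for the table to be populated at all; the point above assumes that the local results enter it.

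**What to change.** In the Lab row of SAP Table 3:

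- cross-tabulate baseline grade, using the protocol 10.6 definition of baseline, against worst post-baseline grade for each selected parameter;
- report the number of subjects whose grade rose above baseline;
- keep the unadjusted worst-grade summary beside it.

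The protocol text need not change, since the SAP governs. No new tests are required: hematology and chemistry are already collected at Screening, and on Cycle 1 Day 1 or within 48 hours before the first dose (protocol sections 8.2.1 and 8.3.1). The cost is one extra table shell. Because the count of rises shows neither within-grade declines nor a return to the baseline grade after improvement, the unadjusted summary should stay.
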